Study Design. The study is a randomized, double blind, placebo controlled clinical trial of HCQ, given 200 mg twice daily, versus placebo for 4 weeks.

Eligibility Criteria

Inclusion:

1. Subjects between the age of 18 and 75, either gender, any ethnic group
2. Subjects must have type 2 diabetes and the following:
 - a. A1c of 6.5-9.0%
 - b. Treated with at least 1000 mg of metformin daily with or without a DPP4 inhibitor, a sulfonylurea (glipizide, glyburide, glimepiride), bromocriptine or coleselam.
3. Subjects should have a BMI >27

Exclusion:

1. Prior treatment with chloroquine or hydroxychloroquine as follows:
 - a. any exposure in the past 2 years,
 - b. >30 days of therapy if exposure was between 2 and 5 years ago,
 - c. >90 days of therapy if exposure was between 5 and 10 years ago,
 - d. >6 months of therapy if exposure was 10 to 20 years ago,
 - e. >1 year of therapy if exposure was 20 to 30 years ago,
 - f. No limit if last exposure was >30 years ago, e.g. during the Vietnam conflict.
2. Morbid obesity (BMI >45)
3. Coronary artery disease or other vascular disease
4. History of stroke
5. Serum creatinine >1.4 mg/dl for women and >1.5 mg/dl for men.
6. Seizure disorder
7. History of psoriasis
8. Hematologic disorders, including anemia (WHO criteria for anemia: hemoglobin <13 g/dL in men and <12 g/dL in women)
9. Current malignancy or active treatment for recurrence prevention, e.g. tamoxifen. Cancer considered to be cured, either as a result of surgery or other treatment is not exclusionary.
10. Asthma requiring daily beta agonist therapy or intermittent oral steroids is exclusionary. Inhaled steroids are acceptable. Obstructive sleep apnea will be allowed if CPAP or other therapy has been stable for 6 months. Other active respiratory diseases are excluded.
11. Treatment with 50mg or greater of Metoprolol or treatment with digoxin
12. Liver disease, or LFTs >2X normal
13. Active infection (including HIV)
14. Serious illness requiring ongoing medical care or medication
15. Treatment with atypical anti-psychotic medication. Treatment with any other medication for psychiatric illness, unless on a stable dose for 6 weeks prior to

enrollment. Patients with unstable psychiatric disorders are excluded per the decision of the study MD regardless of medication history.

- 16. Taking any of the following lipid lowering medications: niacin, fibrates, and greater than 1 gm/day of fish oils
- 17. Uncontrolled hypertension (BP >150/90 mm Hg) at enrollment

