The primary endpoint for this experiment is fasting glucose and fasting LDL. Insulin sensitivity determined by clamp is an exploratory aim. Based on the results of Aim 2 of the ARCH study, we expect to show a difference from baseline in fasting glucose and LDL in 15 subjects per group (80% power and $\alpha=0.05$). We will therefore plan to study 15 subjects per group. We will compare differences between groups using unpaired two-tailed t tests. An interim analysis will be performed after the first 7 patients in each group have completed the study to check for significant differences or refine the sample size.

Anticipated Results, Alternative Approaches, Potential Problems and Benefits

The anticipated results of the study are that HCQ will reduce fasting glucose and will produce a small reduction in LDL. We also anticipate that HCQ will reduce glucose appearance, also known as hepatic glucose output. Based on our prior studies, no effect on blood pressure is expected. The major unknown in this study is whether HCQ at the clinically used dose of 200 mg bid will have the same effect as chloroquine. It is also not known whether HCQ will have the expected effect in the presence of metformin, since the drugs appear to have similar mechanisms of action. The LDL lowering effect of chloroquine was mild in the ARCH study, but not all patients were taking statins, and the mean LDL was higher than is commonly seen in patients with diabetes who are treated to lower LDL targets than non-diabetics. Therefore, the effect size of HCQ on LDL is unknown in this patient population. The results of this mechanistic study will be informative for the planning of future clinical trials of HCQ in persons with diabetes. The hyperinsulinemic clamp are considered to be the gold standard tests for mechanistic studies of the metabolic defects in diabetes, and thus do not have comparable alternatives.

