- An adverse event that would impact any of the study results occurs. An example would be a patient who develops poison ivy during the study and requires oral steroids for control of the rash. Efforts will be made to adjust the study schedule to permit recovery, but if that is not possible or likely, the patient will be withdrawn.

Possible benefits to study patients include satisfaction of altruistic values and a small stipend of \$25 for screening visit and \$175 for clamp visits, for a total of \$375. All study related testing and the investigational agent will be provided at no cost.

Quality Control (Study Monitoring)

The study will be reviewed for safety, privacy and data integrity by the study investigators and staff at regular intervals during the course of the study. Safety data will be shared at regular intervals with the non-engaged safety monitors and any issues will be addressed as appropriate by PIs, sub-I, study staff and HRPO.

The PIs and/or sub-I will monitor each subject's lab results and visit data at each study visit. Subjects will be requested to contact study staff if any event occurs between clinic visits and this information will be reviewed by the PIs.

The PIs will remove any subject at his or her discretion based upon personal judgment or in the event of undue AE's. The PIs will review and report all AE's and report as per HRPO policy. Any new risks or safety issues identified will be reviewed and forwarded to HRPO for review and, if necessary, the study will be stopped. Participants will be notified of any changes that might affect their decision to participate.

Study personnel will enter subject data into a database and/or spreadsheet for analysis. The analysis data sets will be a combination of these data and data from other sources (e.g., laboratory data). In all cases, subject PHI will not be collected in the database. Any information entered into databases will be stored on a secure server, which is password protected and accessible only to authorized study staff.

In accordance with applicable regulations, GCP, and HRPO requirements, the PIs will review with the study staff the protocol, study requirements, and their responsibilities to satisfy regulatory, ethical, and HRPO requirements.

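### The interim analysis at 7 per group has no boundary, final-level adjustment or resizing rule, so the stated alpha of 0.05 is not secured

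*Combined protocol and SAP*

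**What the plan says.** Under Sample Size Estimates and Statistical Analyses, the plan sets 15 participants per group at 80% power and alpha 0.05: "we expect to show a difference from baseline in fasting glucose and LDL in 15 subjects per group". The analysis is then given in one sentence: "We will compare differences between groups using unpaired two-tailed t tests". The interim follows directly: "An interim analysis will be performed after the first 7 patients in each group have completed the study to check for significant differences". Its full purpose has two parts: "check for significant differences or refine the sample size".

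The plan is silent on these points:
- the significance level at the interim, and any change to the final level;
- how the sample size would be changed (from the SD or from the observed difference), and within what limits;
- what follows if the interim difference is significant;
- who runs and who sees the comparison, although under Study Design "The study is a randomized, double blind, placebo controlled clinical trial of HCQ".

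Elsewhere, Study Termination names only unacceptable risk as a ground for ending the trial. Quality Control (Study Monitoring) gives the non-engaged monitors safety material only: "Safety data will be shared at regular intervals with the non-engaged safety monitors", plus a safety report at half completion. Neither section contains an efficacy rule.

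**The concern.** A test of the primary comparison partway through gives a second chance of a false positive unless the plan says that the early result cannot count or sets a stricter threshold for it. Changing the sample size in the light of the observed difference also disturbs the error rate of an unadjusted final t test. The plan announces both possibilities and regulates neither. The rule could therefore be settled after the interim result is known, and a reader of the final p value could not tell what error rate lies behind it.

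**Working it through.** **Inputs from the plan.** Looks at 7 and 15 per group, unpaired two-sided t tests (12 and 28 degrees of freedom), alpha 0.05. The information fraction at the interim is 7/15 = 0.467, so the correlation between the two test statistics is √(7/15) = 0.683.

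**The plan's own figure.** The 15 per group cannot be reproduced, because no effect size or SD is given. Solved backwards, 80% power at 15 per group with a two-sample t test corresponds to a difference of 1.06 SD. This is an assumption and is used only for power and cost. The fixed-N error rates below do not depend on it.

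**Type I error per endpoint, N fixed at 15 per group.**
- Only the final test counts: 5.0%.
- p<0.05 counts at either look. Under the null, each look rejects in about 5.0% of trials and both reject together in about 1.4-1.5%. So 5.0% + 5.0% − 1.5% ≈ 8.5%. Simulation of the t tests gives 8.5% (3,000,000 trials), and the bivariate normal calculation gives 8.4%. A false claim of benefit occurs in 4.3% of trials instead of 2.5%.

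**Type I error per endpoint, N changed and no interim claim.** The rules, minimums and caps here are assumptions, since the plan has none.

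| Basis for the new N | Limits per group | Type I error |
|---|---|---|
| Observed difference (80% power formula) | minimum 15; cap 20 / 30 / 45 / 60 | 5.5 / 6.0 / 6.4 / 6.6% |
| Within-group SD (target 1.06 SD) | minimum 15; cap 20-60 | 5.1-5.3% |
| Within-group SD (target 1.06 SD) | minimum 8; cap 20-60 | 5.9-6.0% |
| Blinded pooled variance | minimum 15; cap 20-60 | 5.0% |

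A separate normal-approximation check of resizing on the observed result gives 6.0% for a conditional-power rule with 15 to 30 per group. Its worst case is 6.1% for that range and 6.7% for 15 to 60. If p<0.05 at the interim also counts and N is reset from the observed difference, the error is 9-10%.

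**A boundary that restores the level.** The Lan-DeMets O'Brien-Fleming function applied to the two-sided 0.05 spends 2{1 − Φ(1.960/0.683)} = 2{1 − Φ(2.869)} = 0.0041 at the interim, which leaves 0.0483 for the final test. With the planned t tests the simulated error is 5.05%. Power at 1.06 SD is 79.7%, against 80.0% for a single test. Software that applies the function to each tail at 0.025 gives a stricter interim level: 2 × 2{1 − Φ(2.241/0.683)} = 0.0021. The plan should therefore state the actual levels. The boundary does not protect against resizing from the observed difference: with the assumed rules above, the error returns to 5.5-6.6%.

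**Size of an interim estimate.** Significance at 7 per group requires an observed difference above t × √(2/7) = 2.179 × 0.5345 = 1.165 SD. If the true difference is 1.06 SD, the estimates that pass this threshold average 1.41 times the truth, against 1.12 times for a significant final test.

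**The case against.** The best defence is that nothing provides for an efficacy claim at the interim. The plan commits to 15 per group, and Study Termination allows for ending the trial on risk alone. This is a small mechanistic study whose stated use is that "The results of this mechanistic study will be informative for the planning of future clinical trials of HCQ in persons with diabetes". On that reading only the final test counts and the error is 5.0%.

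Much of this stands. A reader might infer that the trial as planned runs at 8.5%, or that it would stop on an interim p<0.05. The documents support neither: they do not say that an interim p<0.05 is a claim or a stopping rule. Even the between-group reading of the interim test is inferred, from the preceding sentence on t tests and the words about each group; the powering sentence speaks of change from baseline.

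A reader might also infer that the trial's effect estimate will be overstated about 1.4-fold. That applies only if the interim estimate is reported or the trial stops there. If the trial continues to a fixed 15 per group, the look does not select the final estimate. Even with stopping at p<0.05, the mean estimate over all trials would be about 1.10 times the truth at 1.06 SD.

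Nor do the documents show that the team will be unblinded. The sentence "Study personnel will enter subject data into a database and/or spreadsheet for analysis" concerns data entry. All that can be said is that nobody is named to run or see the interim comparison.

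The defence does not close the gap. Looking for significant differences is a purpose stated in the plan itself, the look is definite, and resizing from the observed difference raises the error even with no interim claim. The mechanistic aim does not remove the commitment to alpha 0.05 and 80% power.

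**Conclusion.** The point holds as an underspecification that should be fixed. The stated look, test and alpha do not together secure 5% per endpoint. The error is 5.0% if only the final test counts at an unchanged 15 per group, about 8.5% if p<0.05 counts at either look, and about 5.5-6.6% if N is reset from the observed difference without an interim claim. The first two figures follow from the plan's own numbers under normally distributed data; the third rests on assumed resizing rules. The case for a change rests on the missing rule, not on the 8.5% reading being the intended one. Multiplicity from having two primary endpoints is a separate matter and is not included.

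**What to change.** Before the interim, replace the sentence with one written rule.

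1. **Simplest: no efficacy claim at the interim.** State that only the final t test at 15 per group counts and that N will not be changed from the observed group difference. Error is 5.0% with N kept at 15, and no extra patients are needed. The cost is that no early claim is possible.

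2. **If an efficacy look is wanted.** Fix a group-sequential boundary, for example p<0.0041 at the interim and p<0.0483 at the end. State what a crossing leads to, do not resize from the observed difference, and have the comparison run by someone who neither sees nor treats participants. Error is about 5.05% and the power loss about 0.3 percentage points at an assumed 1.06 SD. The costs are the need for that person, and a crossing for benefit that is rarer (11% against 45% at p<0.05) and whose estimate is more overstated (1.71-fold against 1.41-fold).

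3. **If resizing is wanted.** Use a blinded pooled-variance review after 14 completers in total, because a trigger of 7 in each group requires knowledge of allocation. State the target difference and the minimum and maximum N beforehand. Error stays at 5.0% per endpoint and the final test is unchanged. There are two costs. The sponsor must supply a target difference for each endpoint: the documents give none, and they call the LDL effect size unknown in this population. The blinded variance also contains any treatment effect, so N tends to rise. At an assumed 1.06 SD with minimum 15, mean N is about 18 per group (cap 20) or 20 (cap 30) for one endpoint. It is about 19 or 23 if the larger requirement of two independent endpoints governs, and less if they are correlated.
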